4.4.2.2 The New Dyadic Peer Support Component

The dyadic peer support component included one dyad peer support training session, dyads working together on their goals for nine weeks, and two group sessions during the nine weeks. Participants also received weekly newsletters. The purpose of using dyadic peer support to augment an existing health promotion program was twofold. First, evaluations from past Faithful Families Thriving Communities programs showed participants want additional health promotion programming once the standard FF curriculum is complete. Second, using existing networks and resources to promote health

increases the possibility of successful program implementation and behavior change (Aschbrenner et al., 2016; Eng & Hatch, 1991; Leahey, LaRose, Fava, & Wing, 2011). Existing resources in this program were faith communities (i.e. relationships among members, available goods and services) and the longstanding relationship between the North Carolina Cooperative Extension offices and the faith communities. At the end of the first nine weeks, participants either chose or were assigned a partner if they did not have a preference. Partners were assigned by the lay leaders and PI based on any relationship they had prior to the program, or developed during the classes – evidenced by repeatedly choosing to sit next to one another and talking during classes.

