4.4.3 Participants and Setting

The inclusion criteria for churches were faith communities with predominantly African American members in one of three counties served by Expanded Food and Nutrition Education Program (EFNEP) nutrition educators. Participant criteria were adults ages 18 years and older who identify as African American; reported being church members or regular church goers; speak, read and write English; willing to complete

study activities and assessments; and able to engage in moderate physical activity. (e.g., walking – based on their own activity level and assessment).

This feasibility study captured qualitative and quantitative data. Data from qualitative interviews generally reaches information saturation between 10-15 interviews (Guest, Bunce, & Johnson, 2006). Thus, a sample size of 20 dyads or 40 participants was planned to ensure data saturation and account for an attrition rate of 30%, as found in a meta-analysis of weight loss programs (Lemstra, Bird, Nwankwo, Rogers, & Moraros, 2016). Also, because statistical significance is not the aim of this feasibility study, a sample size of 40 was considered sufficient to allow insights into patterns of change for quantitative outcomes such as weight and physical activity (Leahey & Wing, 2012; O'Brien et al., 2015). Due to great interest, 80 members across the three sites (site one – 18 members, site two – 24 members, site three – 38 members) were enrolled.

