4.6.3 Goal Attainment Health Outcomes (Aim 2)

Unconditional means models were run for each outcome and the intraclass correlation was calculated to assess for dyad dependence. A three-level mixed model (participants nested within dyads over time) was used to assess changes in weight, BMI,

systolic blood pressure, fruit and vegetable intake, and physical activity. Both unadjusted and adjusted models were run. Church site, dyad relationship (i.e., friend, family or acquaintance), dyad assignment (whether dyads chose or were assigned their partner), and participant characteristics (age, sex, education) were added as model covariates. Dependence of participants during the second nine weeks was accounted for by creating a dichotomous variable to separate measurements taken before participants were paired and measurements taken after they were paired.

First, significant changes from baseline to 18 weeks were assessed. Second, significant changes during the first nine weeks before participants were paired, compared to the second nine weeks after they were paired, were assessed. Third, three interaction terms were entered into three different models to assess whether or not dyad relationship type, dyad partner assignment, or dyad communication frequency influenced changes in health outcomes while participants were paired. Additional descriptive statistics were generated to assess the proportion of participants who were able to achieve clinically significant weight loss (weight loss $\geq 5\%$ of body weight) (Leahey, Kumar, Weinberg, & Wing, 2012; West, Coulon, Monroe, & Wilson, 2016) as well as the recommended servings of fruits and vegetables and daily minutes of physical activity.

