4.6.4 Dyadic Cooperation (Aim 3)

Directed content analysis (Hsieh & Shannon, 2005) was used to analyze semi structured interviews. Deductive a priori coding guided by the TGDM was used to analyze dyad cooperation. Inductive coding was used to analyze participant's perceptions of program feasibility, and the influence of social and environmental factors that influenced their health. Transcripts were read and re-read to identify and

assign codes. Codes were grouped according to themes. Ten percent of transcripts were read by a second reviewer to compare codes, resolve discrepancies in coding, and interpret results.

Table 7. *Assessment Variables and Timeline*

Aim	Variable	Week Assessed	Analysis Method
Participant Characteristics	Participant characteristics	1(Baseline)	Descriptive statistics
Participant Characteristics	Baseline differences between church sites	1	ANOVA, Fisher's exact
Participant Characteristics	Baseline differences between those who did and did not complete the program	1	T-test
Feasibility	Church and participant recruitment and retention	1-18	Descriptive statistics
Feasibility	Feasibility Survey Scores, Dyad communication frequency	18	Descriptive statistics
Goal Attainment/Health Outcomes	Changes in FVI and PA and interactions	1, 9, 18	Mixed Model
Goal Attainment/Health Outcomes	Changes in SBP, BMI, weight and interactions	1, 9, 14, 18	Mixed Model
Feasibility; Goal Attainment; Dyad Interactions	Perceptions of feasibility, dyad interactions - challenges and strategies	18	Directed Content Analysis

- American Heart Association. (2014). Body mass index in adults. Retrieved from <https://www.heart.org/en/healthy-living/healthy-eating/losing-weight/bmi-in-adults>
- American Heart Association. (2017a). The facts about high blood pressure. Retrieved from <https://www.heart.org/en/health-topics/high-blood-pressure/the-facts-about-high-blood-pressure>
- American Heart Association. (2017b). Suggested servings from each food group. Retrieved from <https://www.heart.org/en/healthy-living/healthy-eating/eat-smart/nutrition-basics/suggested-servings-from-each-food-group>

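### The plan does not say how the three moderator interaction terms are built; if each is a single product over all listed visits, about half of any week 1–9 difference in change is counted as paired-phase change

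*Combined protocol and SAP*

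**What the plan says.** Section 4.6.3 sets out three steps for Aim 2: change from baseline to week 18, the first nine weeks compared with the second nine, and moderators. For the third step, "three interaction terms were entered into three different models to assess whether or not dyad relationship type, dyad partner assignment, or dyad communication frequency" mattered for change after pairing. The question put to the data is whether each of these "influenced changes in health outcomes while participants were paired". That is one interaction term per moderator, each in its own model.

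The base model is described as follows: "A three-level mixed model (participants nested within dyads over time) was used to assess changes in weight, BMI" and the other outcomes. The form of time is not given. A phase variable is defined by "creating a dichotomous variable to separate measurements taken before participants were paired and measurements taken after they were paired". Its stated purpose is to account for dependence between partners, and it is not linked to the interaction terms.

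Table 7 has a row "Changes in FVI and PA and interactions" at weeks 1, 9 and 18, and a row "Changes in SBP, BMI, weight and interactions" at weeks 1, 9, 14 and 18. Section 4.4.1 places pairing at the end of the first nine weeks, so weeks 1 and 9 both precede it.

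Relationship type and partner assignment are listed among the adjusted-model covariates in section 4.6.3. Communication frequency is not.

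**The concern.** The third step asks about change after pairing, that is, from week 9 on. A model with a moderator main effect and one product term has only one parameter for how moderator groups diverge over the whole schedule. It cannot separate divergence during the classes (weeks 1–9) from divergence while paired. Using the before/after variable does not solve this, because the reference then becomes the average of weeks 1 and 9 and not week 9 itself.

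Class-phase divergence by moderator is conceivable. Section 4.4.2.2 says that assigned partners were matched on a prior relationship or on one formed during the classes, "evidenced by repeatedly choosing to sit next to one another and talking during classes". Moderator status may therefore reflect engagement in the classes.

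If the groups did diverge in weeks 1–9, a moderator unrelated to paired-phase change could appear to influence it, or a real association could be masked if the class-phase difference ran the other way. These interactions are the plan's quantitative evidence on whether change in health outcomes varies with how dyads are formed or how often partners communicate.

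**Working it through.** The plan states no figure for these models, so there is nothing to reproduce. The check is how much class-phase divergence passes into each form of the term.

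**Inputs.** Visits are from Table 7 and pairing at the end of week 9 is from section 4.4.1. Assumptions: two moderator groups differ by δ in week 1–9 change and by nothing afterwards, so the true paired-phase answer is 0; the moderator main effect is in the model; data are complete with a random intercept. The moderator coefficient then equals a least-squares fit to the group-difference profile, which is (0, δ, δ) at weeks 1, 9, 18 and (0, δ, δ, δ) at weeks 1, 9, 14, 18.

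**Moderator × before/after variable.** Mean after pairing minus mean before: δ − (0 + δ)/2 = 0.50δ on both schedules.

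**Moderator × week**, slope Sxy/Sxx scaled to nine weeks:
- Weeks 1, 9, 18 (mean 9.33): 9 × 8.333/144.667 = 0.52δ.
- Weeks 1, 9, 14, 18 (mean 10.5): 9 × 9.5/161 = 0.53δ.

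**Moderator × weeks since pairing only:**
- Values (0, 0, 9): 9 × 3/54 = 0.50δ.
- Values (0, 0, 5, 9): 9 × 3.5/57 = 0.55δ.

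**Forms with no leak.** Moderator × class-phase slope plus moderator × paired-phase slope, reading the second: 0 on both schedules. Visits from week 9 on only: 0. Categorical visit read as week 18 minus week 9: δ − δ = 0. In a full moderator × week × phase model (four visits), the paired-phase slope difference is 0. The three-way coefficient read alone is not that quantity: it is 0 − 9 × δ/8 = −1.125δ.

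**Constant gap at week 1.** The profile is flat, so the before/after and week products both return 0; the main effect absorbs it.

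**Sensitivity to covariance.** Add a dyad effect that switches on after pairing, with variance 0.2 or 0.7 (assumed; residual 1, person 2). The before/after term stays at 0.50δ, the week term runs from 0.55δ to 0.63δ, and the paired-slope term from 0.46δ to 0.52δ. The two-slope model stays at 0.

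**Dilution of a real effect.** If the paired-phase difference is γ and builds linearly, the before/after term for biometrics averages (5/9 + 1)/2 = 7/9, so it returns 0.78γ + 0.50δ. For FVI and PA it returns γ + 0.50δ.

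**Illustrative false-positive rates.** These are for the FVI/PA before/after term, nominal two-sided 5%, residual SD 1, and two equal groups of n dyads (assumption). Bias is 0.5δ and SE = √[(1.5/2 + τ²) × 2/n], with post-pairing dyad variance τ² = 0 or 0.2. The plan allows sample size to "account for an attrition rate of 30" percent: 80 enrolled × 0.7 = 56 people, 28 dyads, n = 14; 40 planned × 0.7 = 28 people, 14 dyads, n = 7.

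| δ (residual SD) | n = 14 | n = 7 |
|---|---|---|
| 0.25 | 6–7% | 6% |
| 0.5 | 10–12% | 8% |
| 1.0 | 27–33% | 16–19% |

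**Cost in precision (FVI, PA).** Week 18 minus week 9 has a dyad-mean variance of 1.0 + τ², against 0.75 + τ² for the single term. The SE ratio is √(1.0/0.75) = 1.15, or √(1.2/0.95) = 1.12 with τ² = 0.2.

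**The case against.** The strongest reply is that the plan never commits to a single product over all visits. Three terms in three models may only mean one moderator per model. Relationship type has three levels, so its term may already need more than one coefficient, and moderator × categorical visit is also one term. The target is stated in words as change while paired, and a model limited to week 9 onward, or a week 9-to-18 contrast, has no leak. Table 7's weeks may be just the measurement schedule of a merged row. The second step already compares the two phases, so phase-specific time coding may have been available. All of this stands. A reader might infer that the moderator analyses are known to be biased; the documents do not support that, because they do not give the specification.

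It also stands that δ is unknown. The matching rule describes seating and talking, not weight, diet or activity, and it concerns assigned partners only. The false-positive rates do not carry over directly to relationship type or to communication frequency, which is a tally. Nor is there a main effect for communication frequency among the listed covariates, so the fractions apply to that model only if one was entered.

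There is a trade-off too. From the formulas above, the single FVI/PA term has lower mean squared error until 0.25δ² exceeds 0.5/n, that is, δ above √(2/n): 0.38 SD at n = 14 and 0.53 SD at n = 7. Finally, section 4.4.3 says that statistical significance is not the study's aim.

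What remains is that no section restricts these models to week 9 onward or names a paired-phase contrast, and every single-product form examined over the listed visits misses the plan's own question. This is bias in an estimate, so it matters for describing patterns of change as well as for testing.

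**Conclusion.** The point holds conditionally. The composition of the interaction terms and the visits used are not stated. If each term is a single product fitted to all visits in Table 7 with the moderator main effect, 0.50 to 0.55 of any between-group difference in week 1–9 change is read as paired-phase change (random intercept, complete data). The range is 0.46 to 0.63 if a post-pairing dyad variance of up to 0.7 of the residual variance is allowed.

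Two stronger readings should be resisted. Not every difference that predates pairing leaks: a constant gap at week 1 does not, provided the main effect is present. And the second-step comparison of the two nine-week periods is not called into question here.

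The actual bias cannot be given, because the documents do not report δ. The false-positive rates are illustrations for a two-group moderator such as partner assignment. In a single-arm feasibility study with non-randomised moderators, this is a cheap improvement that settles an ambiguity and removes a possible bias.

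**What to change.** In section 4.6.3, state the terms of each moderator model: the moderator main effect, moderator × class-phase slope (weeks 1–9) and moderator × paired-phase slope (week 9 on), with time in weeks and a change of slope at week 9. Enter communication frequency as a main effect in its own model. Interpret only the paired-phase term, with its 95% CI. For FVI and PA, an equivalent is moderator × categorical visit, reporting the week 9-to-18 contrast. Describe the results as associations. For clarity, state the same time scale for the second-step comparison.

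The cost is a few sentences in the plan and three re-specified models, with no new data. The downside is the 12–15% larger standard error for FVI and PA relative to a single before/after term.

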4.6.4 Dyadic Cooperation (Aim 3)

Directed content analysis (Hsieh & Shannon, 2005) was used to analyze semi structured interviews. Deductive a priori coding guided by the TGDM was used to analyze dyad cooperation. Inductive coding was used to analyze participant's perceptions of program feasibility, and the influence of social and environmental factors that influenced their health. Transcripts were read and re-read to identify and

assign codes. Codes were grouped according to themes. Ten percent of transcripts were read by a second reviewer to compare codes, resolve discrepancies in coding, and interpret results.

Table 7. *Assessment Variables and Timeline*

Aim	Variable	Week Assessed	Analysis Method
Participant Characteristics	Participant characteristics	1(Baseline)	Descriptive statistics
Participant Characteristics	Baseline differences between church sites	1	ANOVA, Fisher's exact
Participant Characteristics	Baseline differences between those who did and did not complete the program	1	T-test
Feasibility	Church and participant recruitment and retention	1-18	Descriptive statistics
Feasibility	Feasibility Survey Scores, Dyad communication frequency	18	Descriptive statistics
Goal Attainment/Health Outcomes	Changes in FVI and PA and interactions	1, 9, 18	Mixed Model
Goal Attainment/Health Outcomes	Changes in SBP, BMI, weight and interactions	1, 9, 14, 18	Mixed Model
Feasibility; Goal Attainment; Dyad Interactions	Perceptions of feasibility, dyad interactions - challenges and strategies	18	Directed Content Analysis

- American Heart Association. (2014). Body mass index in adults. Retrieved from <https://www.heart.org/en/healthy-living/healthy-eating/losing-weight/bmi-in-adults>
- American Heart Association. (2017a). The facts about high blood pressure. Retrieved from <https://www.heart.org/en/health-topics/high-blood-pressure/the-facts-about-high-blood-pressure>
- American Heart Association. (2017b). Suggested servings from each food group. Retrieved from <https://www.heart.org/en/healthy-living/healthy-eating/eat-smart/nutrition-basics/suggested-servings-from-each-food-group>
